5.3.2. Meals and Dietary Restrictions

- Participants must abstain from all food and drink (except water) at least 4 hours prior to any safety laboratory evaluations and 10 hours prior to the collection of the predose PK sample on Day 1 of each Period.
- For the fed periods (Treatment E) only, on Day 1, following an overnight fast of at least 10 hours, participants should begin breakfast approximately 30 minutes prior to nirmatrelvir/ritonavir administration. The breakfast will be consumed over approximately a 20-minute interval with nirmatrelvir/ritonavir administered within approximately 10 minutes of completion of the meal. Participants should finish the entire breakfast.
- For the fasted periods (Treatment A;B;C;D) only, on Day 1, following an overnight fast of at least 10 hours, participants should take the medications.
- Water is permitted until 1 hour prior to study intervention administration. Water may be consumed without restriction beginning 1 hour after dosing. Noncaffeinated drinks (except grapefruit or grapefruit-related citrus fruit juices—see below) may be consumed with meals and the evening snack.
- Lunch will be provided approximately 4 hours after nirmatrelvir/ritonavir dosing.
- Dinner will be provided approximately 9 to 10 hours after nirmatrelvir/ritonavir dosing.

- An evening snack may be permitted.
- Participants will refrain from consuming red wine, grapefruit, or grapefruit-related citrus fruits (eg, Seville oranges, pomelos, fruit juices) from 7 days prior to the first dose of study intervention until collection of the final PK blood sample.
- While participants are confined, their total daily nutritional composition should be approximately 55% carbohydrate, 30% fat, and 15% protein. The daily caloric intake per participant should not exceed approximately 3200 kcal.

5.3.3. Caffeine, Alcohol, and Tobacco

- Participants will abstain from caffeine-containing products for 24 hours prior to the start of dosing until collection of the final PK sample of each study period.
- Participants will abstain from alcohol for 24 hours prior to admission (or as specified above for red wine) to the CRU and continue abstaining from alcohol until collection of the final PK sample of each study period. Participants may undergo an alcohol breath test or blood alcohol test at the discretion of the investigator.
- Participants will abstain from the use of tobacco or nicotine-containing products for 24 hours prior to dosing and during confinement in the CRU.

5.3.4. Activity

- Participants will abstain from strenuous exercise (eg, heavy lifting, weight training, calisthenics, aerobics) for at least 48 hours prior to each blood collection for clinical laboratory tests. Walking at a normal pace will be permitted;
- In order to standardize the conditions on PK sampling days, participants will be required to refrain from lying down (except when required for BP, PR, and ECG measurements), eating, and drinking beverages other than water during the first 4 hours after nirmatrelvir/ritonavir dosing;
- Participants will be confined to the procedure room for the first 1 hour after dosing on Day 1 of each period, except to use the bathroom. After this, participants may be ambulatory but should not engage in strenuous activities.

5.4. Screen Failures

Screen failures are defined as participants who consent to participate in the clinical study but are not subsequently enrolled in the study. Screen failure data are collected and remain as source and are not reported on the CRF.

Individuals who do not meet the criteria for participation in this study (screen failure) may be rescreened.

6. STUDY INTERVENTION(S) AND CONCOMITANT THERAPY

Study interventions are all prespecified investigational and noninvestigational medicinal products/auxiliary medicinal products, medical devices, and other interventions (eg, surgical and behavioral) intended to be administered to the study participants during the study conduct.

For the purposes of this protocol, study intervention refers to nirmatrelvir and ritonavir.

6.1. Study Intervention(s) Administered

Study Intervention(s)				
Intervention Name	Nirmatrelvir Tablets	Ritonavir Tablets	Nirmatrelvir Oral Powder	Ritonavir Oral Powder
Arm Name (group of participants receiving a specific treatment or no treatment)	nirmatrelvir/ ritonavir commercial tablets	nirmatrelvir/ ritonavir commercial tablets	nirmatrelvir/ ritonavir oral powder	nirmatrelvir/ ritonavir oral powder
Type	Drug	Drug	Drug	Drug
Dose Formulation	Tablet	Tablet	Powder	Powder
Unit Dose Strength(s)	CCI	[REDACTED]	[REDACTED]	[REDACTED]
Dosage Level(s)	Single dose	Single dose	Single dose	Single dose
Route of Administration	Oral	Oral	Oral	Oral
IMP or NIMP/AxMP	IMP	NIMP	IMP	IMP
Sourcing	Provided centrally by the sponsor	Provided locally by the trial site	Provided centrally by the sponsor	Provided centrally by the sponsor
Packaging and Labeling	Study intervention will be provided in a bulk container for dispensing into individual participant containers by the trial site	N/A	Study intervention will be provided in a bulk container for dispensing into individual participant containers by the trial site	Study intervention will be provided in a bulk container for dispensing into individual participant containers by the trial site
Former name	PF-07321332		PF-07321332	

Study Arm(s)					
Arm Title	Nirmatrelvir/ ritonavir commercial tablets	Nirmatrelvir/ ritonavir oral powder mixed with water	Nirmatrelvir/ ritonavir oral powder mixed with infant formula	Nirmatrelvir/ ritonavir oral powder mixed with vanilla pudding (fasted)	Nirmatrelvir/ ritonavir oral powder mixed with vanilla pudding (fed)
Arm Type	Reference	Experimental	Experimental	Experimental	Experimental
Arm Description	Single oral dose of nirmatrelvir/ ritonavir CCI commercial tablets under fasted conditions	Single oral dose of nirmatrelvir/ ritonavir CCI oral powder mixed with water under fasted conditions	Single oral dose of nirmatrelvir/ ritonavir CCI oral powder mixed with infant formula under fasted conditions	Single oral dose of nirmatrelvir/ritonavir CCI oral powder mixed with vanilla pudding under fasted conditions	Single oral dose of nirmatrelvir/ ritonavir CCI oral powder mixed with vanilla pudding under fed conditions

Nirmatrelvir CCI tablets and nirmatrelvir oral powder will be supplied to CRU in bulk along with individual dosing containers for unit dosing.

Ritonavir oral powder will be supplied to CRU in bulk along with individual dosing containers for unit dosing

Commercially available ritonavir CCI tablets will be sourced by the CRU.

Vehicles (infant formula and vanilla pudding) for nirmatrelvir and ritonavir oral powder administration will be sourced by the CRU.

6.1.1. Administration

Study interventions will be administered orally and according to the conditions described in the SoA section and Protocol Section 5.3.2 Meals and Dietary Restrictions.

Doses taken under fasted condition: On Day 1 of each treatment period, following an overnight fast of at least 10 hours, participants will receive nirmatrelvir CCI (as CCI tablets) with ritonavir CCI (as CCI tablet) with approximately 240 mL ambient temperature water or nirmatrelvir/ritonavir CCI oral powder mixed with either water or infant formula with approximately 210 mL ambient temperature water or nirmatrelvir/ritonavir CCI oral powder mixed with vanilla pudding with approximately 240 mL ambient temperature water administered orally starting at approximately 0800 hours (plus or minus 2 hours). The use of food vehicles for delivery of oral powder are not considered a fed condition. Nirmatrelvir and ritonavir tablets will be dosed simultaneously (within no more than 5 minutes of each other). Participants will swallow all tablet formulations whole and will not manipulate or chew the tablets prior to swallowing. Water will be withheld for 1 hour predose (with the exception of the water consumed as part of the breakfast) and 1 hour after the study treatment administration.

Doses taken under fed condition: On Day 1, following an overnight fast of at least 10 hours, participants will be administered the standard high-fat, high-calorie breakfast approximately

30 minutes prior to the administration of nirmatrelvir/ritonavir oral powder mixed with vanilla pudding. The entire breakfast will be consumed within approximately 20 minutes. The nirmatrelvir/ritonavir **CCI** oral powder mixed with vanilla pudding will be administered 30 minutes after the start of breakfast (allowable window approximately 30 minutes) with 240 mL ambient temperature water. Participants who do not finish the entire meal within approximately 20 minutes or who vomit after consuming the meal will not be dosed resulting in early termination from the study. No additional food will be allowed for at least 4 hours post-dose. Water will be withheld for 1 hour predose (with the exception of the liquid consumed as part of the breakfast) and 1 hour after the study treatment administration.

In order to standardize the conditions on PK sampling days, all participants will be required to refrain from lying down (except when required for BP, PR, and ECG measurements), eating, and drinking beverages other than water during the first 4 hours after nirmatrelvir/ritonavir dosing.

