4. STUDY DESIGN

4.1. Overall Design

This is a Phase 1, open-label, single dose, randomized, crossover study in healthy adult participants to estimate rBA of nirmatrelvir/ritonavir **CCI** [REDACTED] oral powder mixed with 3 different food vehicles (Test formulations) compared to the nirmatrelvir/ritonavir **CCI** [REDACTED] commercial tablets (Reference formulation) under fasted conditions, and to estimate the effect of food on the rBA of the nirmatrelvir/ritonavir oral powder formulation mixed with vanilla pudding. The study will also assess the safety, tolerability, and palatability of nirmatrelvir/ritonavir in healthy adult participants.

Approximately 12 adult healthy male and/or female participants will be enrolled and randomized to 1 of 6 possible treatment sequences. Participants who discontinue from the study for non safety reasons may be replaced at the sponsor's discretion in collaboration with the investigator. The replacement participant will receive the same treatment sequences as the participant who discontinued.

Each enrolled participant will participate in 5 study periods to receive 5 different treatments according to the sequence determined by randomization:

- Treatment A: Single oral dose of nirmatrelvir/ritonavir **CCI** [REDACTED] tablets under fasted condition
- Treatment B: Single oral dose of nirmatrelvir/ritonavir **CCI** [REDACTED] oral powder mixed in water under fasted condition
- Treatment C: Single oral dose of nirmatrelvir/ritonavir **CCI** [REDACTED] oral powder mixed in infant formula under fasted condition
- Treatment D: Single oral dose of nirmatrelvir/ritonavir **CCI** [REDACTED] oral powder mixed in vanilla pudding under fasted condition

- Treatment E: Single oral dose of nirmatrelvir/ritonavir **CCI** oral powder mixed in vanilla pudding under fed condition

Participants will be randomly assigned to 1 of 6 sequences as shown below in Table 3. Participants will be discharged on Day 4 of Period 5, following completion of all assessments. Between each treatment, a minimum of 4 days washout is proposed to minimize any residual nirmatrelvir concentrations prior to start of the next treatment. The total planned duration of participation from the Screening visit to the last follow-up phone call, is approximately 12 weeks.

Table 3. Randomized Treatment Sequences

Treatment Sequence	Period 1	Period 2	Period 3	Period 4	Period 5
Sequence 1 (N = 2)	Treatment A	Treatment B	Treatment C	Treatment D	Treatment E

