Sequence 2 (N = 2)	Treatment B	Treatment C	Treatment A	Treatment D	Treatment E
Sequence 3 (N = 2)	Treatment C	Treatment A	Treatment B	Treatment D	Treatment E
Sequence 4 (N = 2)	Treatment A	Treatment C	Treatment B	Treatment E	Treatment D
Sequence 5 (N = 2)	Treatment B	Treatment A	Treatment C	Treatment E	Treatment D
Sequence 6 (N = 2)	Treatment C	Treatment B	Treatment A	Treatment E	Treatment D

Healthy participants will be screened to determine eligibility within 28 days prior to study treatment. Medical history and results of PE, vital signs, 12-lead ECG, and clinical laboratory evaluations will determine eligibility. Eligible participants will be admitted to the CRU on Period 1 Day -1 and will be confined in the CRU until discharge which is Day 4 of Period 5.

On Day 1 of each period, participants will receive a single oral dose of study interventions nirmatrelvir/ritonavir **CCI** as per the randomization schedule. Study treatments A and D will be administered with approximately 240 mL of ambient temperature water and treatments B and C will be administered with approximately 210 mL of ambient temperature water under fasted conditions (10 hours overnight fast and no food until 4 hours after dosing). Study treatment E will be administered with approximately 240 mL of ambient temperature water approximately 30 minutes after the start of a standard high-fat, high-calorie breakfast. Serial PK samples will be collected up to 72 hours post dose. Participants will be discharged from the CRU on Period 5, Day 4 following completion of all assessments.

If a participant has any clinically significant, study related abnormalities at the conclusion of a scheduled inpatient portion of the study, the Pfizer medical monitor (or designated representative) should be notified and the participant may be asked to remain in the CRU until such abnormalities are deemed not clinically significant, or it is safe for outpatient follow-up.

A safety follow-up call will be made to participants approximately 28 to 35 days from administration of the final dose of study intervention.

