4.4. End of Study Definition

The end of the study is defined as the date of last scheduled procedure shown in the **SoA** for the last participant in the trial.

A participant is considered to have completed the study if they have completed all periods of the study, including the last scheduled procedure shown in the **SoA**.

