9.3.2. Statistical Methods for PK Data

For the primary objective, natural log transformed AUC_{inf} (if data permits), AUC_{last} and C_{max} will be analyzed using a mixed effect model with sequence, period and treatment as fixed effects and participant within a sequence as a random effect. Estimates of the adjusted mean differences (Test-Reference) and corresponding 90% confidence intervals will be obtained from the model. The adjusted mean differences and 90% confidence intervals for the differences will be exponentiated to provide estimates of the ratio of adjusted geometric means (Test/Reference) and 90% confidence intervals for the ratios. For primary objective, Treatment A will be the Reference treatment while Treatments B, C, D and E will be the Test treatments. For food effect estimation (periods 4 and 5 only) Treatment D will be the Reference treatment while Treatments E will be the Test treatment.

PK parameters, including plasma AUC_{inf} (if data permits), AUC_{last} , C_{max} , **CCI** [REDACTED] of nirmatrelvir and ritonavir will be summarized descriptively by treatment. For AUC_{inf} (if data permits), AUC_{last} , and C_{max} , a listing of the individual participant ratios (Test/Reference) will be provided. Box and whisker plots for AUC_{inf} (if data permits), AUC_{last} , and C_{max} , will be plotted by treatment.

The plasma concentrations of nirmatrelvir and ritonavir will be listed and descriptively summarized by nominal PK sampling time and treatment. Individual participant, as well as mean and median profiles of the plasma concentration time data will be plotted by treatment using actual (for individual) and nominal (for mean and median) times respectively. Mean and median profiles will be presented on both linear and semi-log scales.

Additional specifications about the tables, listings, and figures will be outlined in the SAP.

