9.5. Sample Size Determination

A sample size of 12 participants will provide adequate precision to estimate the relative bioavailability and intrasubject variability nirmatrelvir. The following table presents the width of 90% CI for different estimated effects, with 80% coverage probability.

Parameter	Estimated Effect (100%*Test/Reference)	90% CI		CI Width
AUC	85%	78.68	91.83	13.16
	90%	83.30	97.23	13.93
	95%	87.93	102.64	14.71
	100%	92.56	108.04	15.48
	105%	97.19	113.44	16.25
	110%	101.82	118.84	17.03
	115%	106.44	124.24	17.80
C _{max}	85%	76.51	94.43	17.91
	90%	81.02	99.98	18.97
	95%	85.52	105.54	20.02
	100%	90.02	111.09	21.07
	105%	94.52	116.64	22.13
	110%	99.02	122.20	23.18
	115%	103.52	127.75	24.23

These estimates are based on the assumption that within-participant standard deviations are 0.102 and 0.139 for $\ln C_{\max}$ and $\ln AUC_{\text{inf}}$, respectively, as obtained from clinical Study C4671024 in healthy participants.

In addition, a sample size of 12 participants will provide adequate precision to estimate the relative bioavailability and intrasubject variability ritonavir. The following table presents the width of 90% CI for different estimated effects, with 80% coverage probability.

Parameter	Estimated Effect (100%*Test/Reference)	90% CI		CI Width
AUC	85%	72.71	99.37	26.66
	90%	76.98	105.22	28.23
	95%	81.26	111.06	29.80
	100%	85.54	116.91	31.37
	105%	89.81	122.75	32.94
	110%	94.09	128.60	34.51
	115%	98.37	134.44	36.07
	C _{max}	69.29	104.27	34.98
C _{max}	90%	73.37	110.40	37.04
	95%	77.44	116.54	39.09
	100%	81.52	122.67	41.15
	105%	85.60	128.80	43.21
	110%	89.67	134.94	45.27
	115%	93.75	141.07	47.32

These estimates are based on the assumption that within-participant standard deviations are 0.206 and 0.269 for $\ln AUC_{\text{inf}}$ and $\ln C_{\max}$, respectively, as obtained from clinical Study C4671024 in healthy participants.

Participants who withdraw from the study or discontinue treatment, or whose PK samples are considered to be nonevaluable with respect to the primary PK objective may be replaced at the discretion of the investigator upon consultation with the sponsor.

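### A failed Treatment E breakfast ends participation, so Sequences 4–6 also lose the later fasted Treatment D period unless the participant is replaced

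*Protocol*

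**What the plan says.** The fed-condition paragraph of Protocol Section 6.1.1 names two triggers: "Participants who do not finish the entire meal within approximately 20 minutes", or those "who vomit after consuming the meal will not be dosed resulting in early termination from the study". The consequence is the end of study participation, not only the omission of that dose.

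Table 3 in Protocol Section 4.1 fixes the order of D and E. Sequences 1–3 have D in Period 4 and E in Period 5. Sequences 4–6 reverse this, for example "Sequence 4 (N = 2) Treatment A Treatment C Treatment B Treatment E Treatment D". Sections 5.3.2 and 6.1.1 treat D as a fasted treatment and state that a food vehicle does not make the condition fed.

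On the role of D, Section 9.3.2 says "Treatment A will be the Reference treatment while Treatments B, C, D and E will be the Test treatments". D is also the reference for the food effect.

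Replacement is optional in both places that mention it. Section 4.1 covers participants who "discontinue from the study for non safety reasons may be replaced", in the same sequence. Section 9.5 covers withdrawal, stopping treatment or nonevaluable PK samples, and says such participants "may be replaced at the discretion of the investigator upon consultation with the sponsor". Section 4.4 adds: "A participant is considered to have completed the study if they have completed all periods of the study".

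**The concern.** The same event costs different data depending on the randomised order. A participant in Sequences 1–3 who fails the breakfast has already given D. A participant in Sequences 4–6 has completed Periods 1–3 in confinement, can still take D, and is sent home. Neither document explains why D should be cancelled, and neither lets the participant miss E and continue.

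What is lost is one of 12 values of a primary test treatment, for a reason unrelated to D. The individual D/A ratio and that participant's palatability scores for fasted pudding go with it. Section 9.5 states no dropout allowance. No bias is claimed; the cost is precision and an avoidable gap in a 12-participant dataset.

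**Working it through.** **Inputs.** Table 3 layout, 6 sequences × 2 participants. From Section 9.5: 90% intervals with 80% coverage probability at a 100% ratio (nirmatrelvir AUC 92.56–108.04, width 15.48; ritonavir Cmax 81.52–122.67, width 41.15), with within-participant SDs of 0.102 and 0.269.

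**1. Reproducing the plan's intervals.** Limits = 100·exp(±t·s·√(2/12)·√(χ²/df)), with t the 95th percentile of the t distribution and χ² the 80th percentile of the chi-square distribution. The df are not stated; df = 32 fits best, with t = 1.694 and coverage factor 1.096.
- Nirmatrelvir AUC, s = 0.102: 92.56–108.04, as stated.
- Ritonavir Cmax, s = 0.269: 81.55–122.62, against 81.52–122.67 stated.

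The nirmatrelvir rows reproduce only if 0.102 belongs to AUC and 0.139 to Cmax, the reverse of the sentence under the table. That is a separate point.

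**2. Which model can carry D versus A.** A is given only in Periods 1–3, and D and E only in Periods 4–5. With participant, period and treatment effects, 12 + 4 + 4 = 20 parameters are needed but the design has rank 19, and D − A is not estimable even with complete data. The plan's precision formula has no period term, so the loss is measured in a participant + treatment model.

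**3. Variance of D − A.** Let N be the participants with all five treatments and m those with A, B and C only. Within participants, D − mean(A,B,C) has variance (4/3)σ²/N, and A − mean(A,B,C) has variance (2/3)σ²/(N + m). The two are independent, so

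Var(D − A)/σ² = 4/(3N) + 2/(3(N + m)).

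| Case, no replacement | Var/σ² | SE ratio |
|---|---|---|
| Complete, N = 12 | 4/36 + 2/36 = 0.16667 | 1.000 |
| One participant loses E and D | 4/33 + 2/36 = 0.17677 | 1.030 |
| Two lose E and D | 4/30 + 2/36 = 0.18889 | 1.065 |
| E missed, D kept | 2/12 = 0.16667 | 1.000 |

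**4. Scaled widths.** With h = ln(upper/lower)/2 and r the SE ratio, width = 100·(exp(rh) − exp(−rh)), ignoring the small change in df.
- Nirmatrelvir AUC, h = 0.0773: 15.48 becomes 15.94 (one loss) or 16.48 (two).
- Ritonavir Cmax, h = 0.2043: 41.15 becomes 42.40 or 43.85.

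**5. Comparisons involving E.** E is lost under either rule. For E versus A after one event, the SE rises 3.0% under termination. If only E is missed, Var/σ² = (5/4)/11 + (3/4)/12 = 0.17614, a rise of 2.8%. For E versus D in the SAP's D/E-only code, keeping D multiplies the SE by 0.992, 0.996 or 0.999 at assumed intraclass correlations of 0.5, 0.7 or 0.9.

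**6. Frequency.** No meal-failure rate is given. If it were 2%, 5%, 10% or 20% per participant (assumed), the chance that at least one of the six in Sequences 4–6 fails is 1 − (1 − p)⁶ = 11%, 26%, 47% or 74%.

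**The case against.** The strongest reply is that the consequence is slight and mostly already covered.

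- **Margin.** The Section 9.5 widths include the 1.096 coverage factor, so they exceed the expected widths. Without that factor, two unreplaced losses give 1.694 × 0.102 × 0.4346 = 0.0751, a width of about 15.0 for nirmatrelvir AUC. For ritonavir Cmax, 1.694 × 0.269 × 0.4346 = 0.198, a width of about 39.9. Both are inside the tabulated 15.48 and 41.15. This stands: the study's stated precision is not threatened by one or two events.
- **Replacement.** E is also a primary test treatment, so the sponsor has the same reason to replace under either rule. Under the current rule, one termination plus one replacement gives 4/36 + 2/39 = 0.16239, an SE ratio of 0.987, because the first participant's A, B and C data stay in the PK Parameter Set. This stands too, but does not remove the gain. If that participant also gives D, Var/σ² = 2/13 = 0.15385 and the ratio is 0.961. Replacement remains optional, and Section 4.1 limits it to non-safety reasons, which may not clearly cover someone who vomits.
- **Rule clarity.** Termination agrees with the completion definition and spares a participant who cannot supply E another dose and PK period. That is a fair trade-off, but the protocol does not make the argument.
- **Model.** The 3.0% and 6.5% are not from the planned model. True, and unavoidable for the reason in step 2. D values still enter the descriptive summaries, the individual ratios and any corrected primary model.

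**Conclusion.** The point holds as a small, inexpensive improvement. Section 6.1.1 read with Table 3 cancels a fasted D period in Sequences 4–6 after a failed breakfast, without a stated reason and with only optional replacement. Per event without replacement, one of 12 D values is lost and the D/A standard error rises by 3.0% (6.5% for two events), against 0.0% if only E is missed. E versus A and the food effect gain almost nothing.

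The size rests on a participant + treatment model with no period effect and on no replacement. How often the event would occur cannot be judged from the documents. The inability to estimate D versus A with period fixed is a separate problem and is not resolved here.

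**What to change.** In Section 6.1.1, replace the termination consequence with wording such as: *the participant will not receive Treatment E in that period. Failing the meal does not by itself end participation while a fasted period remains; withdrawal for an adverse event is still decided under Section 7.1. The participant may still be replaced for the missing Treatment E data under Section 9.5.*

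Matching edits:
- Section 4.4: say how a participant with an undosed E period is classed for completion.
- Sections 4.1 and 9.5, and SAP Section 2.3 (which repeats 4.1): let replacement cover a participant who stays in the study without E data.

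The cost is one reworded passage in Section 6.1.1 and these short edits. The rule itself requires no extra participants, visits or procedures. The downside is that some participants will have D but no E. Because E versus A is also primary, replacement may still be wanted, and the replacement would repeat treatments the first participant has already supplied.
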